#### 16.1.6. ADVERSE EVENTS OF SPECIAL INTEREST (AESI)

An AESI is any AE for which AE of special interest is indicated as ‘yes’ on the Adverse Events eCRF. Refer to APPENDIX 4: Adverse Events of Special Interest (AESIs) for the list of AEs considered to be of special interest.

The following listing is planned for presentation by treatment group:

- Adverse events of special interest (AESI).

#### 16.1.7. ADVERSE EVENTS LEADING TO PREMATURE STUDY DISCONTINUATION

An AE leading to premature study discontinuation is any AE for which did the AE cause the participant to discontinue from the study recorded as ‘yes’

---

Document: Aeras\_C-040-404\_SAP\_V2\_0  
Author: [name]

Version Number: 2.0  
Version Date: 29SEP2017

Template No: CS\_TP\_BS016 – Revision 3  
Effective Date: 01May2012

Reference: CS\_WI\_BS005

The following listing is planned for presentation by treatment group:

- Adverse events leading to premature study discontinuation.

#### **16.1.8. ADVERSE EVENT (AE) DOSE AT ONSET (MOST RECENT VACCINATION)**

A dose at onset will be assigned for all AEs and is defined as the most recent dose prior to the onset of the AE:

- Post any dose (combination of the AEs starting after the Day 0 and Day 56 vaccinations).
- Post-dose 1 (AEs starting after the Day 0 vaccination).
- Post-dose 2 (AEs starting after the Day 56 vaccination):
  - o Only applicable to H4:IC31 and Placebo treatment groups.

The assignment of the dose at onset will be based on the following algorithm:

- Calculate the difference in the AE start date (as collected on the Adverse Events eCRF) and all available study vaccination dates (as collected on the Exposure Day 0 and Exposure Day 56 eCRFs):
  - o Days since dose x: (AE start date – study vaccination dose x date [where x= 1 or 2]).
- From the previous calculation, only consider those doses where the days since dose x is  $\geq 0$  and determine the dose (1 or 2) for which the days since dose x (as calculated in the previous step) is a minimum.
- Assign the dose selected in the previous step as the dose at onset as the specific dose determined in the previous calculation.

#### **16.1.9. ADVERSE EVENT (AE) POST-VACCINATION REPORTING WINDOW**

All SAEs and AESIs will be collected through database lock.

All unsolicited AEs will be collected during the 28-day reporting window following each study vaccination. The reporting window is defined in terms of the relevant scheduled study visit coinciding with the 28-day window following the relevant dose.

Solicited systemic adverse events will be collected during the 7-day reporting window following each study vaccination (diary cards will be used for 7 days following each study vaccination for the Safety and Immunogenicity Cohort only).

Solicited and unsolicited local injection site reaction adverse events will be collected:

- BCG treatment group:
  - o 84-day reporting window following study vaccination.
- H4:IC31 and Placebo treatment groups:
  - o 28-day reporting window following each vaccination.

---

Document: Aeras\_C-040-404\_SAP\_V2\_0  
Author: [name]

Version Number: 2.0  
Version Date: 29SEP2017

Template No: CS\_TP\_BS016 – Revision 3  
Effective Date: 01May2012

Reference: CS\_WI\_BS005

Refer to Table 4: General Adverse Event (AE) Post-vaccination Reporting Windows below for the relevant post-vaccination reporting windows as defined in terms of scheduled study visits:

**Table 4: General Adverse Event (AE) Post-vaccination Reporting Windows**

Adverse Event Type	Treatment Group	Dose at Onset	Post-vaccination Reporting Window	
			Scheduled Study Visit	Protocol Specified Visit Window
Unsolicited AE	All	Day 0	Study Day 28	28 days following Study Day 0
	H4: IC31 Placebo	Day 56	Study Day 84	28 days following Study Day 56
Local Solicited AEs	BCG	Day 0	Study Day 84	84 days following Study Day 0
	H4: IC31 Placebo	Day 0	Study Day 28	28 days following Study Day 0
	H4: IC31 Placebo	Day 56	Study Day 84	28 days following Study Day 56
Systemic Solicited AEs	All	Day 0	Study Day 7	7 days following Study Day 0
	H4: IC31 Placebo	Day 56	Study Day 63	7 days following Study Day 56
SAEs and AEs of special interest	All	All	-	Through database lock

If the relevant scheduled study visit occurred within the protocol specified visit window, all AEs with start date through the relevant scheduled study visit will be included in the reporting period. If the relevant scheduled study visit occurred outside the protocol specified visit window, only include AEs with start date through either 7, 28 or 84 days will be included.

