There is considerable experience with BCG vaccine, which is licensed in South Africa for prevention of TB in children and adults. Local and systemic reactogenicity in various populations is well described (FitzGerald 2000; Hoft et al 1999; Lotte et al 1984; Nicol et al 2002). Injection site and regional complications, such as extensive local ulceration, local subcutaneous abscesses, and suppurative lymphadenitis, occur in less than 1 per 5 million vaccinations. Induration and redness of the skin at the site of intradermal BCG vaccination typically develops within several days and represents a normal response to BCG vaccination. The induration gradually resolves over several days and is followed by a small local superficial ulcer. The ulcer opens and drains for 4 weeks on average, and spontaneously heals within 2-3 months, usually leaving a small scar. A brief period of minor, asymptomatic enlargement of the regional cervical and axillary lymph nodes (< 1 cm) is common. Systemic adverse events due to BCG occur very infrequently. Fever, headache and non-injection site cutaneous manifestations occur in less than 1% of vaccinees. Severe systemic adverse events, such as osteitis and disseminated BCG disease, are rare (about 1 per 5 million vaccinations) and usually occur in immune-compromised infants. Severe local or systemic complications of BCG would not be expected in the healthy, HIV-uninfected, *Mtb* uninfected adolescents to be recruited in this trial.

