**Table 3-4 Adverse Event Collection Periods**

Type of Event	Collection Period
Unsolicited adverse events	28 days post each vaccination a
Solicited adverse events	7 days post each vaccination (with diary cards to be used for 7 days after each vaccination for Safety & Immunogenicity Cohort only)
Solicited and unsolicited injection site reaction adverse events	BCG Group: 84 days post vaccination AERAS-404/Placebo Groups: 28 days post each vaccination a
Serious adverse events, adverse events of special interest, and SUSARs	Entire study period
a. Adverse events will be collected through the end of the study visit window for each adverse event collection period (i.e., 28 days after each vaccination + 5-day window = 33 days)	

For this study, solicited adverse events to be collected include the following: pain, redness and swelling at the site of injection; fever; myalgia; arthralgia; fatigue; headache; anorexia; hives; and chills. Solicited injection site reaction adverse events include (in addition to pain, redness, and swelling) ulceration, drainage, and axillary lymphadenopathy. Solicited adverse events of local injection site reactions (i.e., pain at injection site, redness at injection site, swelling at injection site, ulceration at the injection site, or drainage at the injection site) will be considered causally related to study injection (adverse reaction). Adverse events of special interest (see Appendix D) will be collected passively during participant safety evaluations.

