## 5.7 Solicited Adverse Events and Injection Site Reactions

Solicited adverse events are events the subject is specifically asked about. These adverse events are commonly observed soon after receipt of vaccines. For this study, solicited adverse events to be collected include: pain, redness and swelling at the site of injection; fever; myalgia; arthralgia; fatigue; headache; anorexia; hives; and chills. Solicited injection site reaction adverse events include (in addition to pain, redness, and swelling) ulceration, drainage, and axillary lymphadenopathy. Solicited adverse events of local injection site reactions (i.e., pain at injection site, redness at injection site, swelling at injection site, ulceration at injection site, or drainage at injection site) will be considered causally related to study vaccine (adverse reaction).

**The reporting period during which *solicited* adverse events will be evaluated is specified in Section 3.** The solicited adverse event reporting period begins with the day of vaccination. All subjects in the Safety & Immunogenicity cohort will be provided a diary card to record temperature and information regarding occurrences of these specific events for the 7 days post-vaccination (see further details in Section 5.16).

Adverse events and solicited adverse events including assessment of local injection site reactions will be assessed by the investigator for severity, causal relationship to the study vaccine, possible etiologies, and whether the event meets criteria as a serious adverse event (and therefore requires immediate notification to the medical monitor).

Presence of ulceration and/or scarring at the site of injection and axillary lymphadenopathy of the injection arm(s) are considered to be adverse events that are causally related to the study vaccine and are of special interest. Site of injection ulceration (including presence of drainage) and axillary lymphadenopathy will be actively evaluated during through Day 84. These events will be recorded on the Adverse Event CRF as applicable.

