### 16.1.2. ALL ADVERSE EVENTS (AEs)

The following tables are planned for presentation:

- Overview of AEs:
  - o Number and percentage (%) of participants in each of the following categories (participants with multiple events in each category are counted only once in each category):
    - Any AE.
    - Any solicited AE.
    - Local solicited AE.
    - Systemic solicited AE.
    - SAE.
    - SAE with outcome of death.
    - Related AE.

---

Document: Aeras\_C-040-404\_SAP\_V2\_0

Author: [name]

Version Number:

2.0

Version Date:

29SEP2017

Template No: CS\_TP\_BS016 – Revision 3

Reference: CS\_WI\_BS005

Effective Date: 01May2012

Copyright © 2012 Quintiles Transnational Corp. All rights reserved.

The contents of this document are confidential and proprietary to Quintiles Transnational Corp. Unauthorized use, disclosure or reproduction is strictly prohibited.

- Severe AE.
- Related, severe AE.
- AE leading to premature study discontinuation.
- Adverse events of special interest (AESI).
- Percentage (%) of participants will be calculated relative to the total number of participants in the Safety analysis set per treatment group and cohort.
- 95% CIs:
  - Calculated for single proportion using mid-p binomial option (Clopper-Pearson method with mid-p correction).
- Number of events in each of the aforementioned categories (participants with multiple events in each category are counted multiple times in each category).
- This output will be repeated for the Safety and Immunogenicity Cohort as well as the Correlates Cohort.

All AE incidence tables will be sorted by:

- SOC (descending frequency of total number of participants with events reported).
- PT (descending frequency of total number of participants with events reported within each SOC).

All AE incidence tables presented by PT only will be sorted by:

- PT (descending frequency of total number of participants with events reported).

The following incidence table will be presented by SOC and PT:

- Incidence of AEs:
  - Number and percentage (%) of all participants with AEs summarized by SOC and PT.
  - Includes all AEs within the post-vaccination reporting windows (refer to Section 16.1.9: Adverse Event (AE) Post-vaccination Reporting Window for details on the derivation of post-vaccination reporting window).
  - This table will be repeated for the Safety and Immunogenicity Cohort.

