### 16.1.4. SOLICITED AND INJECTION SITE ADVERSE EVENTS (AEs)

In the database all AEs were reported as either solicited or unsolicited, however the database categorization will not be used to report AEs as either solicited or unsolicited. All AEs will be assigned as either solicited or unsolicited based on the PT (refer to APPENDIX 3: Solicited and Injection Site Adverse Event (AE)) and post-vaccination reporting window (refer to Section 16.1.9: Adverse Event (AE) Post-vaccination Reporting Window for a description of the post-vaccination reporting windows).

Local and systemic solicited AE incidence tables will be presented as follows:

- Solicited AE category (local, systemic).
- PT (descending frequency of total number of participants with events reported within each solicited AE category).

The following incidence tables will be presented by PT only:

- Incidence of solicited AEs.
- Incidence of related solicited AEs.
- Incidence of related solicited AEs by dose at onset (refer to Section 16.1.8: Adverse Event (AE) Dose at Onset (Most Recent Vaccination) for details on the derivation of dose at onset):
  - o Number and percentage (%) of participants with AEs summarized by solicited AE category and PT.

---

Document: Aeras\_C-040-404\_SAP\_V2\_0  
Author: [name]

Version Number: 2.0  
Version Date: 29SEP2017

Template No: CS\_TP\_BS016 – Revision 3  
Effective Date: 01May2012

Reference: CS\_WI\_BS005

- o Includes all solicited AEs within the post-vaccination reporting window (refer to Section 16.1.9: Adverse Event (AE) Post-vaccination Reporting Window for details on the derivation of the post-vaccination reporting window).
- o BCG treatment group will only include Dose 1 at onset AEs.
- Incidence of solicited AEs per cohort and dose at onset (refer to Section 16.1.8: Adverse Event (AE) Dose at Onset (Most Recent Vaccination) for details on the derivation of dose at onset):
  - o Number and percentage (%) of participants with AEs summarized by solicited AE category and PT.
  - o Includes all solicited AEs within the post-vaccination reporting window (refer to Section 16.1.9: Adverse Event (AE) Post-vaccination Reporting Window for details on the derivation of the post-vaccination reporting window).
  - o BCG treatment group will only include Dose 1 at onset AEs.
- Incidence of local solicited AEs by severity and dose at onset:
  - o Number and percentage (%) of participants with AEs summarized by solicited AE category and PT.

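### SAP 16.1.9 contradicts itself on unsolicited BCG injection-site events: its text gives them 84 days, but Table 4 gives them 28, so later-onset events could drop out of two safety tables in the BCG arm only

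*SAP*

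**What the plan says.** **Collection.** Protocol Table 3-4 has a line for "Solicited and unsolicited injection site reaction adverse events" with the period "BCG Group: 84 days post vaccination". The other two arms have 28 days after each dose. General unsolicited AEs have 28 days after each vaccination in every arm.

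**SAP text.** Section 16.1.9 first gives all unsolicited AEs a 28-day reporting window. It then makes a specific statement, opening "Solicited and unsolicited local injection site reaction adverse events will be collected", and sets an 84-day reporting window for the BCG group.

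**SAP Table 4.** The same section refers to Table 4 for the windows by scheduled visit. The row for unsolicited AEs applies to all groups after Day 0, is tied to the Study Day 28 visit, and reads "28 days following Study Day 0". (The same words also appear in the H4:IC31/placebo row for local solicited AEs; the unsolicited row is the one at issue.) The single 84-day row is for local solicited AEs in BCG. No row covers unsolicited injection-site events.

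**Classification.** SAP 16.1.4 sets aside the category in the database: "All AEs will be assigned as either solicited or unsolicited based on the PT", together with the reporting window. The Appendix 3 local terms for BCG are lymphadenopathy and vaccination site pain, erythema, swelling, ulcer and discharge.

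**Tables.** For the incidence table by system organ class and preferred term, SAP 16.1.2 states: "Includes all AEs within the post-vaccination reporting windows". The unsolicited overview in SAP 16.1.3 carries the same limit.

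**The concern.** A BCG site event whose preferred term is not in Appendix 3 is classed as unsolicited, whatever the site recorded. Section 16.1.9 then gives two answers for when it stops counting: the Day 84 visit (text) or the Day 28 visit (Table 4). Table 4 is the form a programmer is likely to work from.

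Safety of BCG revaccination is a primary objective. Protocol 7.5.1 makes the primary safety variable the solicited and unsolicited AEs recorded at all available time points after vaccination. Protocol 5.7 treats scarring at the injection site as causally related and of special interest, and Protocol 1.6 says the BCG ulcer heals in 2 to 3 months and usually leaves a small scar. Scar is not an Appendix 3 term and is not in the SAP Appendix 4 list of AESIs. Abscess and lymphadenitis are not in Appendix 3 either.

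The omission can only lower counts, and only in the BCG arm. It could also leave the incidence table out of step with the AE overview, which states no window.

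**Working it through.** The point concerns reporting windows, so no alpha, power or event count enters it. The check is day arithmetic plus a reading of which tables carry the limit.

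**Inputs**
- BCG Day 28 visit: 28 ± 5 days from Day 0, i.e. Day 23 to Day 33 (Protocol Appendix A).
- BCG Day 84 visit: 84 ± 7 days from Day 0, i.e. Day 77 to Day 91 (Protocol Appendix A).
- Inclusion rule (below SAP Table 4): if the visit is in window, AEs starting up to the visit date count; otherwise the cut-off is the fixed 7, 28 or 84 days.

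**1. The plan's own figure.** The footnote to Protocol Table 3-4 puts the end of the 28-day period, with its visit window, at 33 days: 28 + 5 = 33. Reproduced.

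**2. Span left uncovered if Table 4 is followed.** Uncovered days = Day 84 cut-off − Day 28 cut-off.

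| Day 28 cut-off | Day 84 cut-off | Uncovered days | Share of the longer window |
|---|---|---|---|
| 28 (nominal) | 84 (nominal) | 84 − 28 = 56 | 56/84 = 66.7% |
| 33 (latest) | 77 (earliest) | 77 − 33 = 44 | 44/77 = 57.1% |
| 23 (earliest) | 91 (latest) | 91 − 23 = 68 | 68/91 = 74.7% |

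The gap can begin as early as Day 24 or as late as Day 34. Onsets on Days 29 to 33 are kept when the Day 28 visit is late but in window.

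**3. Other arms.** For H4:IC31 and placebo, the local and unsolicited windows are both 28 days after each dose. 28 − 28 = 0 days lost.

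**4. Which events are exposed.** Windows use the AE start date.
- Ulcer, discharge, lymphadenopathy, pain, erythema and swelling are Appendix 3 terms and keep 84 days.
- Induration is not listed, but Protocol 1.6 says it develops within several days, so its usual onset is inside 28 days.
- Scar is not listed. With the SAP's 4-week month, healing at 2 to 3 months is 2 × 28 = 56 to 3 × 28 = 84 days, beyond the latest Day 28 cut-off of 33.
- For "extensive local ulceration, local subcutaneous abscesses, and suppurative lymphadenitis", Protocol 1.6 gives a rate below 1 per 5 million vaccinations. For 330 planned BCG subjects that is under 330/5,000,000 = 0.000066 expected events.

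**5. Which outputs are exposed.**

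| Output | Window stated? |
|---|---|
| Incidence by SOC and PT (16.1.2) | Yes |
| Unsolicited overview (16.1.3) | Yes |
| AE overview, incidence by dose, incidence by PT only (16.1.2) | No |
| By highest severity (16.1.2.1) | No |
| Related AEs (16.1.2.2) | No |
| Listing of solicited and unsolicited non-serious AEs (16.1.2) | No |

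The solicited tables in 16.1.4 carry a window too, but these events are not solicited terms. SAEs and flagged AESIs run through database lock in Table 4.

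**The case against.** The strongest defence is that the 84-day window is already in the SAP. The specific sentence in 16.1.9 covers unsolicited local reactions and calls the period a reporting window; 16.1.2 and 16.1.3 point to the section as a whole; and Table 4 is headed as general. A careful programmer could follow the specific sentence and lose nothing. This stands in part: the exclusion is conditional on Table 4 being followed. It does not remove the contradiction, because the same text also gives all unsolicited AEs 28 days, and Table 4 is what turns the text into visit-based rules.

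Three stronger readings are tempting and are not supported:
- A reader might infer that these events have no window at all. The text gives them one; Table 4 conflicts with it.
- A reader might infer that they would appear only in a listing. The AE overview and several other tables state no window, and scarring, deemed causally related by Protocol 5.7, would belong among the related AEs.
- A reader might infer that the local events which Protocol 1.6 and 5.7 single out are removed. Most are not: ulceration, drainage and axillary lymphadenopathy are covered by Appendix 3 terms.

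It is also fair to say that 67% is a share of days, not of events, and that the Protocol's own rate makes abscess and suppurative lymphadenitis negligible here. Both stand. The practical weight rests on scarring and any other unlisted site term with late onset.

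**Conclusion.** The concern holds as an internal contradiction in SAP 16.1.9 with a conditional consequence. If Table 4 is programmed as written, BCG injection-site events with unlisted preferred terms and onset after the Day 28 visit (Day 23 to 33), up to the Day 84 visit (Day 77 to 91), are left out of two tables: incidence by system organ class and preferred term, and the unsolicited overview. Nominally that is 56 of 84 days, with a range of 44 to 68 days when both visits are in window. Only the BCG arm is affected.

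The number of events cannot be derived, since the documents give no rate for scarring recorded as an AE. The practical effect assumes that sites recorded a scar as its own AE rather than as a sequela of the ulcer, that it was coded outside Appendix 3, and that it was not flagged as an AESI on the case report form. The documents therefore do not support a claim that BCG safety will be materially understated. They do support correcting the table, because the contradiction affects a primary safety objective and can act in one direction only.

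**What to change.** 1. Add a row to SAP Table 4: unsolicited injection-site AEs; BCG; dose at onset Day 0; Study Day 84 visit; 84 days after Day 0.
2. Restrict the 28-day unsolicited row, and the matching general sentence in 16.1.9, to non-injection-site events in the BCG arm.
3. List the preferred terms that count as unsolicited injection-site or regional-node events, for example scar, abscess, induration and lymphadenitis.
4. Produce the 16.1.2 incidence table and the 16.1.3 overview under the amended table.

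The cost is one row, one wording change and a short term list. No new data are needed, since BCG injection-site events are already collected at the Day 70 and Day 84 visits. The downside is a slightly higher BCG local AE count.

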## 16.2. INJECTION SITE REACTION ASSESSMENT

Injection site reaction assessments will be presented for the Safety analysis set.

The following injection site reaction assessment listing is planned for presentation:

- Injection site reaction assessment.

The following injection site reaction variables will be collected throughout the study on the eCRFs:

- Date and time of assessment.
- Injection site reaction assessment:
  - o Pain.
  - o Redness.
  - o Swelling.
  - o Ulceration.
  - o Drainage.
  - o Abnormality photo taken.
  - o Axillary lymphadenopathy.

Document: Aeras\_C-040-404\_SAP\_V2\_0

Author: [name]

Version Number:

2.0

Version Date:

29SEP2017

Template No: CS\_TP\_BS016 – Revision 3

Reference: CS\_WI\_BS005

Effective Date: 01May2012

Copyright © 2012 Quintiles Transnational Corp. All rights reserved.

The contents of this document are confidential and proprietary to Quintiles Transnational Corp. Unauthorized use, disclosure or reproduction is strictly prohibited.

- Present:
  - o Yes:
    - Measurement (mm) for relevant assessments.
  - o No.

